**Cannabidiol:**

Subjects will receive 600mg of oral CBD for 3 days in an open-label fashion. Cannabidiol will be provided using Epidiolex™ oral solution 100mg/mL. Drug will be procured by the BWH Investigational Drug Services (IDS) pharmacy. The first dose will be administered at the BWH Center for Clinical Investigation during Visit 2 following the pre-exposure cue-induced cravings assessment, while doses 2 and 3 will be self-administrated at home. The CBD will be repacked in pre-drawn syringes for the subjects to self-administer at home. Cannabidiol will be stored at room temperature (68 to 77 F) in its original bottle and in an upright position. Once opened, Cannabidiol has a shelf life of 84 days.

[figure not shown]
	Baseline	Pre-exposure + open-label CBD 600mg (dose 1)	Open-label CBD 600mg (doses 2 and 3)	Post-exposure
Study visit number	1	2	Home administration	Home administration
Psychiatric History Self-Report				
Pregnancy test				
PHQ-9				
GAD-7				
BPI				
LFTs				
PANAS				
COWS				
Urine toxicology				
Cue-induced craving, anxiety, and pain scales				
General craving, anxiety, and pain scales			Drug diary	Drug diary
Adverse effects			Drug diary	Drug diary
Physiologic monitoring (vital signs)				
Quantitative Sensory Testing (QST)				
TLFB				

**Figure 1: Cue-induced craving assessment**

Cue-induced craving procedure: Participants will be presented with a series of 20 heroin-specific or neutral images. Images will be presented on a computer using a timed stimulus presentation on Microsoft PowerPoint. Participants will view both presentations (heroin-specific and neutral) for one minute each, and after presentation of all images will complete the paper-and-pencil ratings of opioid craving, anxiety, and pain scales. This task is anticipated to take between 10-15 minutes to complete, depending on participant speed of responding. Participants will complete a standardized relaxation procedure after completion of the cue-reactivity test.

[figure not shown]
Quantitative Sensory Testing (QST) Procedure: QST consists of two parts: 1) Pressure pain threshold and tolerance, determined by a pressure algometer; 2) Temporal summation, measured using repeated mechanical pinprick.

- 1) Pressure pain threshold: Pressure algometry is the most commonly used test for static mechanical pressure sensation in the skin and in deep tissues. Pressure algometers deliver a firm and quantifiable pressure through a flat base applied to the skin. The electronic pressure algometer that we will use (Wagner Instruments) is a hand-held algometer utilizing a pressure-sensitive strain gauge, covered by a 0.5 cm^2 circular probe. The probe is covered with a soft polypropylene disk, to avoid injury to the skin. The pressure applied through the probe is transduced, amplified, and converted to electrical reading on a digital display. The pressure will be slowly increased (1 lb/s) and the participant will be asked to note when they first feel pain and when they want the pressure to stop, which will be recorded as the pressure pain threshold and tolerance, respectively. This process will be repeated on the trapezius and the forearm, alternating between sides of the body with 20 seconds between measurements.
- 2) Temporal summation testing methods: Mechanical pinprick pain will be assessed in a similar manner to our previous studies, using standardized weighted pinprick applicators similar to those described by Rolke et al, using a range of forces (128 mN, 256mN and 512mN) which result in a painful sensation in most subjects. First, a single stimulation of the lower force pinprick will be applied to the dorsal aspect of the index finger between the first and second interphalangeal joints of each hand while resting palm down on a flat surface such as a table or armrest, and then rated by the subject on

a scale of 0-10. The weight probe that induces at least some pain, but not more than 3/10 pain will be determined, and this probe used for repeated testing. After a break of at least 10 seconds, a train of 10 stimuli will be applied at the same spot, at a rate of 1 stimulation/second. The subject will rate pain on a scale of 0-10 after the first, fifth and tenth stimulus, then rate any ongoing pain 15 seconds after cessation of the last stimulus (painful aftersensations). Temporal summation will be calculated as the change in pain score between the highest and lowest pain ratings in a train.

**Alternative approach for temporal summation of pain assessment:** Tonic, deep-tissue, mechanical stimulation will be applied using a rapid cuff inflator (Hokanson) wrapped around the leg, centered around the middle of the gastrocnemius muscle in a similar manner to our previous studies. Pressure will then be increased at approximately 5-10 mmHg/s, at which time participants will be asked to note when they first start feeling pain and then when they feel as though the pain is a 4/10. At this point the cuff will be deflated. Participants will be given a 30 second break. The cuff will be re-inflated to this previously identified pressure and held for two minutes (or until participant asks to stop), at which point the cuff will be deflated. Participants will be asked to rate their pain every 30 seconds, as well as to rate any painful after sensations after cuff deflation. Temporal summation will be calculated as the change in pain score between the highest and lowest pain ratings in the 2 minutes.

**Figures 2 and 3** below summarize the schematic order of Visit 2 (Pre-exposure) and Visit 3 (Post-Exposure), respectively.

**Figure 2:** Study Visit 2 Schema

**Figure 3:** Study Visit 3 Schema

**Compensation:** Participants will be reimbursed for travel/parking, \$100 for completing the baseline visit, \$50 for completing visit 3, and \$100 for completing visit 3 (\$250 total for completing all visits).

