**Individual differences in pain processing and central sensitization:** Psychophysics, which is the careful and systematic testing of sensory processing in humans in a laboratory setting, with standardized equipment and protocols, has revealed important differences amongst individuals taking opioid analgesics, including higher pain sensitivity. Specifically, central sensitization is a process by which the spinal nociceptive system responds to sustained noxious peripheral input by amplifying the transmission of this signal, and has proven to be an important mechanism in the development of chronic pain in preclinical research. A clinical correlate of central sensitization is temporal summation of repetitive painful stimuli. Importantly, variability in temporal summation, measured by the increase in pain sensation during a sequence of stimuli, is observed among individuals and groups and may indicate an individual's endogenous analgesic response. Temporal summation has been shown to distinguish differences between low- and high- opioid users, and risk for opioid misuse. By including a quantitative sensory testing (QST) assessment of both pressure pain threshold/tolerance and temporal summation of pain (TSP) in this study, we will gain valuable pilot data on: (1) how much patients with OUD on buprenorphine exhibit central sensitization, and how they may differ from chronic pain patients and healthy volunteers (from our other studies); and (2) how CBD impacts central sensitization, by performing a pair-wise comparison of temporal summation of pain of patients before and after they begin taking CBD.

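### Temporal summation is scored as highest minus lowest rating, which ignores direction, cannot be negative and is inflated by rating noise

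*Combined protocol and SAP*

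**What the plan says.** Section I (individual differences in pain processing and central sensitization) describes temporal summation as "measured by the increase in pain sensation during a sequence of stimuli". It gives the measure two uses. One is to show how far patients on buprenorphine exhibit central sensitization, including against chronic pain patients and healthy volunteers from the group's other studies. The other is to assess the effect of CBD "by performing a pair-wise comparison of temporal summation of pain of patients before and after they begin taking CBD".

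Section V (temporal summation testing methods) sets the scoring. A probe is chosen first: "The weight probe that induces at least some pain, but not more than 3/10 pain will be determined". Ten stimuli follow, and "The subject will rate pain on a scale of 0-10 after the first, fifth and tenth stimulus". A separate aftersensation rating is taken 15 seconds after the last stimulus. The rule is then: "Temporal summation will be calculated as the change in pain score between the highest and lowest pain ratings in a train". The alternative cuff method, with ratings every 30 seconds, is scored as the "change in pain score between the highest and lowest pain ratings in the 2 minutes".

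Section VI (biostatistical analysis) does not mention temporal summation, so the Section V rule is the only one in the plan.

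**The concern.** An increase has a direction; highest minus lowest does not. Neither scoring sentence requires the highest rating to come after the lowest. Followed as written, the rule counts falling pain as summation and turns random variation in the ratings into a positive score.

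Both stated uses are exposed. The first is an estimate of level, which an always-positive noise term pushes upward, most where true summation is small. The second is a change within patients. There the range can shrink or hide a real directional change, and it can respond to a change in how consistently patients rate rather than in how much their pain builds up. Section VI says the pilot's main interest is in effect sizes and variance for a larger trial. A compressed effect with a noise-dependent offset would be a poor planning input for this measure.

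**Working it through.** The plan gives no figure for temporal summation, so there is none to reproduce.

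**Inputs**
- Three ratings per train (stimuli 1, 5 and 10) on a 0-10 scale: Section V.
- Starting pain above 0 and at most 3/10: Section V. I use 3, with a check at 2.
- 10 subjects and a two-sided paired t-test at 0.05: borrowed from Section VI, where they apply to craving.
- Rating SD: not in the documents. Assumed 0.3, 0.5, 0.7, 1.0 and 1.5, independent between ratings.
- No between-subject spread in the true profile: assumed.

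**Step 1: algebra, no assumptions.** Let R = max(y1, y5, y10) - min(y1, y5, y10) and S = y10 - y1. R is never below 0.

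| Ratings | R (plan) | S (signed) |
|---|---|---|
| 1, 2, 3 | 2 | +2 |
| 3, 2, 1 | 2 | -2 |
| 2, 4, 2 | 2 | 0 |

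**Step 2: flat pain.** For three independent normal ratings with SD s, the mean of R is (3/√π) × s = 1.69s. That is 0.85, 1.69 and 2.54 points at s = 0.5, 1.0 and 1.5. For the cuff it is 2.06s with four ratings, or 2.33s with five if one is taken at time 0. Simulated with whole-number ratings limited to 0-10 (400,000 trains per setting, true profile 3, 3, 3):

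| Rating SD | 0.3 | 0.5 | 0.7 | 1.0 | 1.5 |
|---|---|---|---|---|---|
| Mean R | 0.27 | 0.81 | 1.18 | 1.69 | 2.51 |
| Mean S | 0.00 | 0.00 | 0.00 | 0.00 | 0.00 |

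Starting at 2/10 instead gives 0.81, 1.67 and 2.37 at SD 0.5, 1.0 and 1.5.

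**Step 3: pain that truly changes.** With a true rise of 2 (3, 4, 5), R averages 2.0 at SD 0.3 and 3.06 at SD 1.5. With unbounded ratings and a true rise of 3, the excess is 0.01, 0.22 and 0.68 at SD 0.5, 1.0 and 1.5. At SD 1.0 a true rise of 1 and a true fall of 1 both score 1.90.

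**Step 4: before versus after** (40,000 studies of 10 subjects; same noise at both visits unless stated).

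| True situation | Change in R | Change in S |
|---|---|---|
| Flat at both visits | 0.0; test rejects 4-5% | 0.0 |
| +1 to 0 | -0.78 (SD 0.3) to -0.16 (SD 1.5) | -1.0 |
| +1 to -1 | 0.0 | -2.0 |
| +2 to +1 | -0.95, -0.83, -0.70 (SD 0.3, 0.5, 0.7) | -1.0 |
| +3 to +2 | about -1.0, -0.95, -0.89 (SD 0.3, 0.5, 0.7) | -1.0 |
| Flat; SD falls from 1.0 to 0.7 | -0.51; test rejects 20% | 0.0; rejects 5% |

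The signed score varies more between subjects: for a flat train at rating SD 0.7, its SD is 1.07 against 0.75. That does not cancel its advantage. For the true change from +1 to 0, power at SD 0.5, 0.7 and 1.0 is 22%, 10% and 6% with R, and 69%, 46% and 27% with S.

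**The case against.** The strongest reply is that the two sections differ only for flat, falling or noisy trains. If ratings rise steadily, highest minus lowest is the increase. With a true change from +3 to +2 the range loses little: power is 98% against 98%, 67% against 69%, and 42% against 46% at SD 0.3, 0.5 and 0.7. At a true +2 and SD 0.5 or less, the level is overstated by at most 0.06 points. This stands and limits the size of the problem. It does not remove it, because the study cannot know beforehand that its patients show strong summation; how much they show is one of the questions.

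Every size above rests on an assumed SD and independent ratings. Noise shared by all ratings in a train cancels from the range. The fall in noise from 1.0 to 0.7 is an illustration, not a prediction. This also stands, but the direction of the bias and the results in Step 1 need no such figure.

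The range may have been chosen to match the other studies, whose scoring the documents do not show. That is a reason to report the range as well for that comparison, not to rely on it alone.

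Tenth minus first ignores the fifth rating and so misses a mid-train peak. The cuff hold may also end early, so its last rating can fall at different times at the two visits. The first is a real cost of a simple score. The second affects the range too.

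Finally, the aftersensation is arguably excluded already, since it follows the train. Saying so outright costs nothing.

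**Conclusion.** The concern holds. The scoring rule does not measure what Section I describes: it discards direction, cannot fall below zero, and has a positive mean when nothing but rating noise is present. These properties need no assumption beyond some variation in the ratings.

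Their size depends on the assumed SD of 0.3 to 1.5. The overstatement of level is 0.27 to 2.51 points for flat pain and slight where pain clearly rises. Before versus after CBD, the rule creates no false effect when noise and profile are the same at both visits. It weakens small true changes, hides a reversal of direction, and can respond to a change in rating consistency alone. The simulations assume a common true profile for all subjects.

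Temporal summation is a secondary pilot measure. The primary craving outcome and its sample size are unaffected. The rule should be corrected, but it does not threaten the main result.

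**What to change.** Replace the scoring sentence in Section V: temporal summation is the rating after the tenth stimulus minus the rating after the first; for the cuff, the last minus the first rating during the 2-minute hold. State that negative values are kept and that the aftersensation rating is not part of the score. Where a cuff hold ends early, record the time of the last rating so that unequal durations are visible.

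The cost is one sentence and no new data, since the first, fifth and tenth ratings are already collected. If the studies used for comparison were scored as highest minus lowest, either rescore them or report the range as well, for that comparison only. Expect a larger between-subject SD for the signed score (1.07 against 0.75 for a flat train at rating SD 0.7) and use that SD when planning the next trial.

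### If the alternative cuff test is used, its highest-minus-lowest score is cut short in subjects who ask to stop early, which can distort the before/after CBD comparison

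*Combined protocol and SAP*

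**What the plan says.** Section V describes two ways to measure temporal summation. The main one is a pinprick train of ten stimuli, rated after the first, fifth and tenth. The other, under the paragraph headed as an alternative approach, is a cuff on the leg.

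For the cuff, pressure is first raised until the subject reports 4/10. After a 30-second break the cuff is re-inflated to that pressure and "held for two minutes (or until participant asks to stop". Pain is rated every 30 seconds, and aftersensations are rated after deflation. The score is defined as follows: "Temporal summation will be calculated as the change in pain score between the highest and lowest pain ratings in the 2 minutes". The text does not ask for a rating at re-inflation or at the moment of stopping. It does not ask for the stop time, and it gives no scoring rule for a shortened hold. Nor does it say when, or for whom, the cuff replaces pinprick.

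Section I gives temporal summation two uses. One is to learn "how much patients with OUD on buprenorphine exhibit central sensitization", compared with chronic pain patients and healthy volunteers from other studies. The other is a paired comparison before and after CBD. Section VI contains no analysis or missing-data rule for quantitative sensory testing (QST).

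For pinprick, the probe is chosen by this rule: "The weight probe that induces at least some pain, but not more than 3/10 pain will be determined, and this probe used for repeated testing". The forces are 128, 256 and 512 mN.

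**The concern.** The number of ratings behind a cuff score depends on what the score is meant to measure. A subject whose pain climbs quickly, or who tolerates it poorly, stops sooner and contributes fewer ratings. A highest-minus-lowest score cannot show a rise that happened between the last scheduled rating and the stop, and with a single rating it can show no rise at all.

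Two uses are exposed. In the comparison with other groups, steep summators can look like weak ones. In the paired comparison, a subject who holds longer after CBD gains ratings, so the score can go up although the true rise per unit time has gone down. The study exists to supply effect sizes and variances for a larger trial, and with a target of 10 subjects each distorted or missing score is one tenth of the sample. A rating not taken at the stop cannot be recovered afterwards.

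**Working it through.** **The plan's own figure.** Section VI has the only sample-size figure, and it concerns craving. Taking 1.5 as the SD at each time point with r = 0.60, the SD of the change is 1.5 × √(2 × (1 − 0.60)) = 1.342, and the standardised change is 1.5/1.342 = 1.118. With n = 10 and two-sided alpha 0.05, the noncentral-t power is 88.1%, which reproduces the stated 88%. Nothing below bears on it.

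**Ratings available (from the text).** A stop at T seconds leaves the whole-number part of T/30 scheduled ratings, plus one if a time-0 rating is taken.

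| Stop | Ratings, no time 0 | Ratings, with time 0 |
|---|---|---|
| before 30 s | 0 (no score) | 1 (score 0) |
| 30–59 s | 1 (score 0) | 2 |
| 60–89 s | 2 | 3 |
| 90–119 s | 3 | 4 |
| full 120 s | 4 | 5 |

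**Illustration (assumptions, not in the documents).** Pain rises linearly from 4/10 at both visits, and the subject stops on reaching 9/10. For a rise of s points per 30 s, stop time = (9 − 4)/s × 30 s, up to 120 s.

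| s | Hold | Scheduled ratings | Score, no time 0 | Score, with time 0 | Rise reached |
|---|---|---|---|---|---|
| 0.5 | 120 s | 4.5, 5, 5.5, 6 | 1.5 | 2.0 | 2.0 |
| 0.75 | 120 s | 4.75, 5.5, 6.25, 7 | 2.25 | 3.0 | 3.0 |
| 1 | 120 s | 5, 6, 7, 8 | 3.0 | 4.0 | 4.0 |
| 1.5 | 100 s | 5.5, 7, 8.5 | 3.0 | 4.5 | 5.0 |
| 2 | 75 s | 6, 8 | 2.0 | 4.0 | 5.0 |
| 3 | 50 s | 7 | 0 | 3.0 | 5.0 |
| 6 | 25 s | none | none | 0 | 5.0 |

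**If CBD halved the rise:**

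- 1.5 to 0.75: 3.0 to 2.25 (with time 0, 4.5 to 3.0). Right direction.
- 2 to 1: 2.0 to 3.0, reversed. With time 0, 4.0 to 4.0, a tie.
- 3 to 1.5: 0 to 3.0, reversed. With time 0, 3.0 to 4.5, still reversed.
- 6 to 3: no score, then 0. With time 0, 0 to 3.0, reversed.

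Without a time-0 rating, reversal needs s above 5/3 ≈ 1.67, which is a baseline stop before 90 s. With one, and for s up to 5 (a stop at 30 s or later), reversal occurs only for s between about 2.5 and 3.3. Slopes of about 1.67 to 2.5 and 3.3 to 5 tie, and smaller slopes go the right way.

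**Other stopping levels.** Comparing s = 1 with s = 2.5, the scores without a time-0 rating are 2.0 against 0 (stop at 7/10), 3.0 against 0 (8/10), and 3.0 against 2.5 (9/10 and 10/10). The slower riser scores higher each time. With a time-0 rating they are 3.0 against 2.5, 4.0 against 2.5, then 4.0 against 5.0 twice, so the order is wrong only at the two lower levels.

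**Noise.** With independent, equal-variance normal rating error and no true rise, the expected range of 1 to 5 ratings is 0, 1.13, 1.69, 2.06 and 2.33 SD. A longer hold therefore raises the score even where nothing summates.

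**The case against.** The strongest objection is that the cuff may never be used. The opening of the QST procedure defines temporal summation by repeated pinprick, and the pain-testing paragraph of Section VII names only the algometer and the pinprick probes. The pinprick train has a fixed length and no comparable early-stop rule. This stands, and it makes the point conditional.

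Second, the size of the distortion depends on chosen slopes. That also stands. Subjects who complete the hold at both visits are compared in the right direction. If hold time is equal at both visits, much of the bias cancels in the paired difference. The slow riser at 0.5 outscores the fast riser at 3 only without a time-0 rating (1.5 against 0); with one, the order is right (2.0 against 3.0). A reader might infer that the CBD comparison will have the wrong sign. The documents support only that it can, under the conditions above.

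Third, a reader might infer that the rules drop or under-score the most pain-sensitive subjects generally. The documents do not support this:

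- Cuff pressure is set to each person's own 4/10, so an early stop points to a steep rise or low tolerance, not to a low pain threshold.
- For pinprick, the protocol does not say that a subject without a qualifying probe is excluded. It is silent, and the cuff could be the fallback, although no switching rule is written.
- The window of some pain but at most 3/10 can fail at both ends: above 3/10 at 128 mN, or no pain at 512 mN.
- High pain from one prick is not the same as a rise over a train, so a downward bias in pinprick summation is not shown.

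Finally, QST is absent from the Study Aim and from Section VI. This limits the weight of the point, but Section I still assigns the measure two comparisons.

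**Conclusion.** The point holds for the cuff method, if it is used. From the text alone, a stop before 60 s gives a score of 0 or none (before 30 s, a score of 0, if a time-0 rating is taken), and a later stop can miss part of the rise. The score can therefore be biased low in steep summators and in subjects with low tolerance. The before/after CBD comparison can be distorted, and in some cases reversed, when hold time differs between visits.

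The numerical size rests on an assumed linear rise from 4/10 and an assumed fixed stopping level. In that model a true rise of 5 points within 50 s scores 0, or 3.0 with a time-0 rating. The documents give no frequency of early stopping, so the average bias cannot be stated. The measure is exploratory, and the primary outcome and the 88% power are unaffected. The change is worth making before any cuff data are collected.

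For pinprick the point is only a minor clarification of the probe rule.

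**What to change.** If the cuff is kept as an alternative:

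1. Take a pain rating at re-inflation (time 0) and another at deflation, whether at two minutes or at an earlier stop, and record the hold time.
2. Include both ratings in the highest-minus-lowest score.
3. Report hold time at each visit alongside the rise. This is necessary because, in the illustration, slopes of 3 and 1.5 then both score 5.0 and differ only in hold time (50 s and 100 s). Halving no longer reverses in the cases shown: 1.5 to 0.75 gives 5.0 to 3.0, 2 to 1 gives 5.0 to 4.0, and 3 to 1.5 and 6 to 3 tie at 5.0.
4. As a supplement, report a rate: (last rating minus time-0 rating) divided by total hold time. For slopes 3, 1.5 and 0.5 this gives 5/50 × 30 = 3.0, 5/100 × 30 = 1.5 and 2/120 × 30 = 0.5 per 30 s, the right order. It is less stable for short holds (a 1-point error over 15 s becomes 2 points per 30 s), so it should not stand alone.
5. Keep the score as now written alongside, for comparison with earlier studies.

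The cost is two extra ratings and one recorded time per cuff test, plus a few sentences. The new scores will not be identical to the laboratory's earlier ones. The subject's right to stop is unchanged.

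Separately, state what is done when no pinprick probe falls in the window, at either end.
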